 - Vitals at (Treatment Period 5, Day 0) predose (T-0), intradose after the start of study drug IV infusion (SEL-037) at 15, 30, 45, 60, 90, 120 and 180 minutes, then at 6 hours; and then at Day 1, 7, 14, 21 and 30 or early termination.
 - ECG exam at (Treatment Period 5, Day 0) predose and End of Study Treatment Period 5, Day 30 or early termination.

Statistical methods:

Data will be listed and summarized as appropriate. Descriptive statistics at each dose level (number of subjects, arithmetic mean, standard deviation, geometric mean, coefficient of variation, median, minimum and maximum, as appropriate) will be used to summarize the PK and safety results by dose groups. The PK and PD relationship will be explored.

Table 2: Schedule of Events, Cohorts 1 & 2, Part B - Treatment Periods 4-5

Cohorts 1 & 2 Phases:	Out patient	In Clinic										Outpatient Follow-up Visits					
	V21	V22										V23	V24	V25	V26	P5 D21 to D30	Early Term / EOS P5 D30 ^{8,10}
Treatment Period #4; Visit (V); Day (D); Period (P)	P4 D-1	P4 D0 ⁸ (28 days after P3 D0)										P4 D1	P4 D7	P4 D14	P4 D21		
Treatment Period #5; Visit (V); Day (D); Period (P)	V27	V28										V29	V30	V31	V32		
	P5 D-1	P5 D0 ⁸ (28 days after P4 D0)										P5 D1	P5 D7	P5 D14	P5 D21		
Hour (h)	Pre-dose	Infusion (time after dosing started)				Post-infusion (time after dosing started)					PK at ±2h from D0 0h ⁹	PK blood draws should occur at same time each visit ± 8 h from D0 0 hour ⁹					
		0h	0.25h	0.5h	0.75h	1h	1.5h	2h	3h	6h	9h						
Informed Consent																	
Dual Energy CT Scan																X	X
Inflammatory Markers																X	X
T-Cell Recall												X ¹¹					
Demographics																	
Inclusion/exclusion	X																
Medical History ¹	X																
Safety Examinations	Pre-dose	0h	0.25h	0.5h	0.75h	1h	1.5h	2h	3h	6h	9h						
Physical Examination																	X
Concomitant medications		←----- continuous ----->															
Vital signs ²	X	X	X	X	X	X	X	X	X	X	X	X	X	X	X	X	X
ECG ³	X																X
Adverse Events - Rheumatology CTC		←----- continuous ----->															
Safety Labs	Pre-dose	0h	0.25h	0.5h	0.75h	1h	1.5h	2h	3h	6h	9h						
Safety Labs - As indicated in individual schedules ⁴	X													X			X
Immunogenicity																	
Anti-Pegsiticase	X												X	X	X	X	X
Anti-Uricase	X												X	X	X	X	X
Anti-PEG	X												X	X	X	X	X
PK/PD Assessments																	
SEL-110 PK																	
SEL-037 PK	X											X	X	X	X	X	X

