10.1.1. Additional Observational Visit

We have noted in the open label portion of the SEL-212/101 clinical trial and the initial portion of this SEL-212/201 clinical trial a persistent and beneficial effect on serum uric acid (sUA) when subjects are given SEL-212. This effect had persisted beyond 30 days in 17 of 31 subjects as of November 28, 2016. Based on these results, our goal is to follow subjects in Cohorts 3-8, 10, 11, and 12 beyond the current protocol Treatment Period 5, Day 30 Visit so that we may monitor and characterize the continued effect of SEL-212. Since there is a lag between lab results and the visits we would propose to see the subject for an additional visit if the sUA at the Treatment Period 5 Day 21 (Visit 32) is below 6 mg/dL. The additional visit would be 60 ± 1 days after the Treatment Period 5 Day 0 dosing day (Visit 28) at which time we would have the value of the sUA for the Day 21 (Visit 32) visit and their end of study visit (EOS P5 Day 30) value. The beneficial effect on the sUA is an unexpected, positive event which is beneficial to the subject and would likely be beneficial to the projected treatment population in the future.

In Part C (Cohorts 13, 15, and 17), subjects will be followed as described above.

Blood samples will be taken at the observational visits for assessments that will include: serum uric acid, and serum samples for anti-pegsiticase, anti-uricase and anti-PEG.

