11.1.3. Weight and Height

Height and weight will be recorded at the Screening Visit. Weight will also be recorded at Day 21 visits for each treatment period, ie. at Visits 8, 14, 20, 26 and 32.

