6. GENERAL ASPECTS FOR STATISTICAL ANALYSIS

6.1. GENERAL METHODS

SAS® version 9.3 will be used for all statistical analyses and tabulations.

In general, summaries will present data by treatment/cohort and assessment time where appropriate. Unless stated otherwise, descriptive summaries will include n, mean, standard deviation, median, minimum, and maximum for continuous variables, and n and percent for categorical variables. If there are multiple assessments collected on the same scheduled time within the windows, the average of these assessments will be used. For tabulated safety summaries, only the scheduled assessments will be included in the summary tables.

Data collected at unscheduled visits will be included in the data listings but will not be included in the analyses. The data for the EOS visit at day 140 will be separated from the Early Termination visit data and will be summarized for all the subjects within the defined population who reached this visit. An additional observational visit for subjects with <6 mg/dL uric acid concentration on day 140 (approx. 30 days after last dose) were scheduled at approx. 170 days from 1st dose. The data for the observational visit will be reported and summarized for all subjects participating in this visit. Data for Early Termination visits will be listed with actual day from dose included and will not be summarized. The last result for repeat test at screening visit will be considered as final and will be included in summaries. Previous results will be listed but not summarized.

Adverse events and medical history will be coded according to the most recent Medical Dictionary for Regulatory Activities (MedDRA) version. Prior and concomitant medications will be coded using the most recent WHO Drug Dictionary version.

Derivation of PK parameters will be performed using Phoenix WinNonLin 6.4 or higher on a Windows 7 platform or higher.

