9.2. COLLECTION SCHEDULE

Venous blood samples with corresponding time post-dose for uric acid are shown in table below:

Cohorts 1-2

Period	Day	Time from start of dose for saline, h	Time from start of dose for SEL-037, h
1-3	0	0	-1 (0)
		1.5	0.5
		2	1
		3	2
		6	5
		9	8
		24	23
		168	167
		336	335
	504	503	
	672	671	
4-5	0	0	0
			0.5
			1
			1.5
			2
			3
			6
1	24		
7	168		

Statistical Analysis Plan

Period	Day	Time from start of dose for saline, h	Time from start of dose for SEL-037, h
	14		336
	21		504
	28**		672
	30***		720

* - pre-dose for next Treatment period

** - PD point for Treatment periods 4 as pre-dose for Treatment period6

*** - last point for Treatment period 5 only

Cohorts 3-8, 10, 11, 12

Period	Day	Time from start of dose for saline, h	Time from start of dose for SEL-037, h
1-3	0	0	-1 (0)
		1	0
		1.5	0.5
		2	1
		3	2
		6	5
		9	8
		1	23
		7	167
		14	335
		21	503
		28*	671
		4-5	0
	0.5		
	1		
	1.5		
	2		
	3		
	6		
1	24		
7	168		
14	336		
21	504		
28**	672		
30***	720		

* - pre-dose for next Treatment period

** - PD point for Treatment periods 4 as pre-dose for Treatment period6

*** - last point for Treatment period 5 only

Statistical Analysis Plan

Cohorts 13, 15

Period	Day	Time from start of dose for saline, h	Time from start of dose for SEL-037, h
1-5	0	0	-1 (0)
		1	0
		1.5	0.5
		2	1
		3	2
		6	5
		9	8
		1	24
		7	168
	14	336	
	21	504	
	28*	672	
	30**	720	

* - pre-dose for next Treatment period

** - last point for Treatment period 5 only

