9.6. DATA PRESENTATION FOR URIC ACID

The actual sampling time of uric acid blood sample collection will be listed for each cohort and will include the deviation in time from the protocol scheduled time, if applicable.

Individual subject serum concentration data and %CFB will be listed by subject, time point, and treatment group (combined placebo or dose group in relevant concentration units) and will be summarized at each time point by cohort. Baseline is defined as the last concentration of uric acid measured before dose for the 1st Treatment period and Cohort separately.

Individual subject PD parameters derived using actual measurements and %CFB will be listed for the PD analysis set in a table by subject and will be summarized, by treatment group (combined placebo or dose group) and cohort.

The table summarizing the number and % of the subjects maintaining sUA levels below 6 mg/dL at the end of treatment period 3 (week 12, visit 22) and at the end of treatment period 5 (Week 20, visit 32) will be produced.

Additionally the sUA concentrations for the week 12, visit 22 will be summarized in separate table including frequency of the subjects with sUA levels <6 mg/dL at this visit for a subset of population meeting the following eligibility criteria;

1. Patients received entire 1st doses (without drug discontinuation)
2. Patients did NOT discontinue due to a withdrawal of consent during Treatment Period 1 or TP2
3. Patients did NOT discontinue due to a protocol deviation during Treatment Period 1 or TP2
4. Patients did NOT discontinue due to NON-study drug related (OR unlikely to be study drug related) SAE during TP1 or TP2

Statistical Analysis Plan

Additionally the sUA concentrations for the week 20, visit 32 will be summarized in separate table including frequency of the subjects with sUA levels <6 mg/dL at this visit for a subset of population meeting the following eligibility criteria;

1. Patients received entire 1st doses (without drug discontinuation)
2. Patients did NOT discontinue due to a withdrawal of consent during Treatment Period 1, TP2, TP3 or TP4
3. Patients did NOT discontinue due to a protocol deviation during Treatment Period 1 or TP2
4. Patients did NOT discontinue due to NON-study drug related (OR unlikely to be study drug related) SAE during TP1 or TP2

The following figures will be produced for Uric Acid:

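### SAP 9.6 ties the end-of-Period-5 uric acid rate to a week and a visit that cannot be the same sample: Visit 32 is Period 5 Day 21 (Week 19), while Week 20 falls at the End of Study visit.

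*SAP*

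**What the plan says.** SAP 9.6 asks for the number and percentage of subjects whose sUA is under the 6 mg/dL threshold on two occasions. The first is given as "at the end of treatment period 3 (week 12, visit 22"; the second is given as "at the end of treatment period 5 (Week 20, visit 32". Two subset tables repeat the pairings of week 12 with Visit 22 and week 20 with Visit 32. SAP 9.3 defines the same two counts by the end of the period only, with no visit or day.

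The visits are fixed elsewhere:

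- **Visit 22.** The protocol's schedules of events make it Period 4 Day 0, "28 days after P3 D0". SAP 9.2 describes the Day 28 uric acid sample as "pre-dose for next Treatment period" and gives Day 30 as the last sample of Period 5.
- **Visit 32.** Protocol 11.1.3: "Weight will also be recorded at Day 21 visits for each treatment period, ie. at Visits 8, 14, 20, 26 and 32". Protocol 10.1.1 offers the extra observational visit "if the sUA at the Treatment Period 5 Day 21 (Visit 32) is below 6 mg/dL". Protocol 10.5 gives the same day for Visit 32 in Part C.
- **Day 140.** SAP 6.1 places the EOS visit there and describes "An additional observational visit for subjects with <6 mg/dL uric acid concentration on day 140", which is not the Visit 32 value that Protocol 10.1.1 uses.

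Three further rules decide who is counted. Under Protocol 6.3.1, Cohorts 3 and above receive the next dose only if Day 21 sUA is at most 1.0 mg/dL, and Cohorts 1 and 2 have their own Day 21 limit. SAP 6.1 lists Early Termination data without summarizing them. SAP 15.2.5.2 sets the default percentage denominator to subjects with an observation.

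**The concern.** These percentages are the plan's simplest statement of whether control lasts through the monthly dosing interval, which bears directly on the pharmacodynamic objective. As written, the week label and the visit number select different samples, and nothing in SAP 9.3 or 9.6 says which governs. A programmer who follows the visit number will put a 21-day value under a Week 20, end-of-period heading. A subject controlled at Day 21 and uncontrolled by Days 28-30 would then be reported as controlled at Week 20, and the table would set a 28-day reading for Period 3 beside a 21-day reading for Period 5.

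**Working it through.** **Calendar.** Inputs: a treatment period typically lasts 28 days (Protocol 6.3.1), each dosing interval may vary by ±1 day (Protocol 6.1), Visit 32 is Period 5 Day 21, and EOS is Period 5 Day 30 ± 1. Study day = 28 × (period − 1) + day in period; week = study day / 7.

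- Visit 22 (Period 4 Day 0): 28 × 3 = Day 84; 84 / 7 = Week 12.0. The SAP's figure is reproduced.
- Visit 32: 28 × 4 + 21 = Day 133; 133 / 7 = Week 19.0. The SAP's Week 20 is not reproduced.
- Visit 32 at the extremes: 27 × 4 + 21 = Day 129 (Week 18.4) to 29 × 4 + 21 = Day 137 (Week 19.6). It cannot reach Day 140.
- Week 20: 7 × 20 = Day 140 = 112 + 28, that is, Period 5 Day 28.
- EOS: 112 + 30 = Day 142, range 27 × 4 + 29 = 137 to 29 × 4 + 31 = 147, which contains Day 140.
- Visit 20 (Period 3 Day 21): 56 + 21 = Day 77 = Week 11.0.

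Time since dose is therefore 28 days at Visit 22, 21 days at Visit 32 (7 days shorter) and 30 days at EOS (2 days longer).

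**Direction, by illustration.** The documents give no Day 21 or Day 28 rates, so every value here is an assumption. It applies to Cohorts 3 and above, with the same kinetics in both periods. Let *a* = P(Day 21 sUA ≤ 1.0), *b* = P(1.0 < Day 21 sUA < 6), *q* = P(below 6 at Day 28, given Day 21 ≤ 1.0), and 0.5 the same probability given Day 21 between 1.0 and 6.

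- Period 5 read at Visit 32: *a* + *b*
- Period 5 read at Day 28: *aq* + 0.5*b*
- Period 3 at Visit 22, observed subjects only (all passed the Day 21 check): *q*
- Period 3 at Visit 22 over all dosed in the period, stopped subjects counted as not controlled: *aq*

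With *a* = 0.6, *b* = 0.1, *q* = 0.9, these are 70%, 0.54 + 0.05 = 59%, 90% and 54%.

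For (*a*, *b*) of (0.5, 0.1), (0.6, 0.1), (0.7, 0.1), (0.6, 0.2) and (0.8, 0.05), with *q* of 0.8, 0.9 and 1.0, the Visit 32 rate is:

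- about 3 to 22 points above Period 5 at Day 28;
- 5 to 32 points above Period 3 over all dosed;
- from 40 points below to 5 points above Period 3 over observed subjects.

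The first difference keeps its sign throughout. The comparison with Period 3 changes sign with the denominator.

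**The case against.** **The visit number may be the slip.** SAP 9.3 names no visit, SAP 6.1 puts Day 140 at EOS, and SAP 9.5 attaches Visit 32 to a Day 21-30 scanning window, so the SAP uses that visit number loosely. If the EOS sample was meant, Period 5 is read at about 28 to 30 days and the timing difference largely disappears. This stands: the documents do not show which label is wrong. It does not remove the defect, because the pairing recurs in the subset table and leads to different samples.

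**A reader might infer that Period 5 is flattered relative to Period 3**, so that withdrawal of SEL-110 in Parts A and B, or five combination doses in Part C, looks better than it is. The documents do not support that. Visit 22 is a dosing visit reached mainly by subjects who have just passed the Day 21 check, stopped subjects' data are not summarized, and the default denominator is observed subjects. The Period 3 rate could be the inflated one. Visit 32 has no such check within its own period.

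**The evidence on fading is indirect.** Protocol 10.1.1 reports an effect beyond 30 days in 17 of 31 subjects by a cut-off date. Protocol 4.3.2.1, on single-dose SEL-037, reports an effect to Day 7 in all but 1 of 22 subjects and to Day 30 in 1, but also two subjects with very low uric acid at Day 30. Neither source isolates Days 21 to 28, and subjects reaching Period 5 have passed four Day 21 checks. A percentage overstatement cannot be derived from them.

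**Other outputs cover part of the gap.** sUA is summarized at each time point, EOS and observational-visit data are summarized, and SAP 9.7 models Day 21 values in every period. The responder table is descriptive, no listed contrast tests Period 3 against Period 5 responders, and Part C against Part B at Period 5 uses the same visit on both sides. This limits the damage. The percentage below 6 mg/dL at EOS is still not explicitly tabulated.

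**Conclusion.** The pairing of Week 20 with Visit 32 is impossible under the protocol's schedule and should be corrected before programming. What is certain is the calendar: Visit 32 is Week 19 and 21 days after the dose, against 28 days for Visit 22. If the visit number is followed, Period 5 control is probably overstated against its own Day 28-30 value. That rests on the assumption that control tends to fade after a dose, and its size is unknown.

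The two rates are not comparable, for two reasons: the time since dose, and the selection of who reaches Visit 22. Which rate is the higher for these reasons is not established.

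**What to change.** In SAP 9.3 and 9.6, for the main table and the Week 20 subset table:

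1. Define the end of Period 5 as the EOS sample (Period 5 Day 30 ± 1) and pair it with the pre-dose sample at Visit 22.
2. Label Visit 32 as Week 19 (Period 5 Day 21).
3. Add the matched Day 21 pair: Visit 20 (Week 11) and Visit 32 (Week 19).
4. State one denominator for both rates that keeps subjects stopped earlier for loss of uric acid control, and say how they are classified. Their assessments at 30 ± 2 days after the last dose (Protocol 6.3.1) are available for this. The subset criteria do not exclude these subjects, but the default denominator would drop them for lack of an observation.
5. Reconcile SAP 6.1 with Protocol 10.1.1 on which sUA value, Day 140 or Visit 32, defines the observational-visit subset.

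The cost is SAP wording and minor extra tabulation from samples already scheduled. The rates may come out slightly less favourable.

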8.2.2. Management and Treatment of Infusion Reactions

The following steps will be implemented in this protocol to either reduce the risk of infusion reactions or manage infusion reactions.

- Subjects with immunoreactivity to PEG will be ineligible for the study
- Subjects with prior exposure to uricase therapy will be ineligible
- Each subject will be observed for infusion reactions after dosing of study drug in the clinic for 9 hours from the start of study drug infusion (SEL-110 or saline for Part A or SEL-037 for Part B). Subjects will be instructed on the signs or symptoms of infusion reaction and told to notify the PI immediately if they feel they are experiencing one.

- SEL-110 will be administered via syringe pump to control the infusion rate of the small volume of material
- SEL-037 will be administered by slow infusion over an hour only in a healthcare setting and by healthcare providers sufficiently equipped and prepared to manage infusion reactions including anaphylaxis.
- Subjects will be pre-medicated with 180 mg fexofenadine orally two times before dosing and 40 mg methylprednisolone (or equivalent drug) intravenously $-1 \pm 0.5h$ before dosing in an attempt to reduce infusion reactions in subjects.
- Subjects with a history of anaphylaxis, angioedema or previous infusion reactions will be excluded from the trial.
- Only sites with immediate capability to appropriately respond to a reaction of this severity will be allowed to participate in the trial to reduce the risk to any subject

If an infusion reaction occurs, Investigators are allowed to use concomitant medications or treatments deemed necessary to provide adequate subject care. Investigators should also utilize the infusion reaction lab kit (see Appendices) to collect additional blood specimens. In the case of a Grade 3 or 4 infusion reactions occurring during an infusion, the administration of study drug should be immediately discontinued, and the affected subject should be treated according to the clinical trial site's protocol for infusion reactions (e.g., monitoring, administration of antihistamines, corticosteroids, fluids and epinephrine, as clinically indicated).

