11.2.2.5. Action taken with study drug

The action taken in regards to study drug will be assessed by the investigator as:

- Dose not changed (dose completed)
- Dose reduced (IV infusion was modified by subtraction by changing the amount dosed)
- Dose interrupted (IV infusion was temporally modified by temporarily stopping the infusion; slowing of the rate of infusion should also be classified as interrupted)
- Drug withdrawn (IV infusion was modified through termination of the infusion)

A response option for increasing the dose is not an available course of action in this study.

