5.4. PHARMACODYNAMIC ANALYSIS SET

The PD analysis set will include will include all subjects who are randomized, receive any amount of study drug, and have at least one post-baseline assessment of sUA is available. Uric acid concentrations will be listed for all subjects in PD analysis set.

All available PD data will be included in the listings; the PD data will be evaluated for protocol violations or deviations that would significantly affect the PD evaluation of the drug. Profiles or individual time points with such violations or deviations will be flagged and may be excluded from summary statistics and the derivation of PD parameters. Examples to treat as the deviations will be but not limited to:

Statistical Analysis Plan

- 1) Dose interruptions in their SEL-037 dose such that only partial doses were delivered - PD profiles may be excluded from summaries and may be used in analyses with actual dose of SEL-037 used if possible
- 2) Dose interruptions in their SEL-110 dose such that only a partial dose of SEL-110 and/or NO DOSE of SEL-037 was administered (since only SEL-037 will cause sUA to be reduced) - the profiles for the treatment period with deviation will be excluded from summaries and may be used for additional analyses without SEL-037 if needed; the data for prior periods will be included
- 3) Subjects who have a dose interruption during SEL-110 administration in the 1st treatment period and so do not ever receive SEL-037 but do have measured sUA values - as above, may be used for additional analyses without SEL-037 if needed post-hoc.

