15.2.5.2. Table Conventions

- Units will be included where available
- If the categories of a parameter are ordered, then all categories between the maximum and minimum category should be presented in the table, even if n=0 for all treatment groups in a given category that is between the minimum and maximum level for that parameter. For example, the frequency distribution for symptom severity would appear as:

Severity Rating	N
severe	0

Statistical Analysis Plan

moderate	8
mild	3

Where percentages are presented in these tables, zero percentages will not be presented and so any counts of 0 will be presented as 0 and not as 0 (0%).

- If the categories are not ordered (e.g., Medical History, Reasons for Discontinuation from the Study, etc.), then only those categories for which there is at least 1 subject represented in 1 or more groups should be included.
- An Unknown or Missing category should be added to any parameter for which information is not available for 1 or more subjects.
- Unless otherwise specified, the estimated mean and median for a set of values should be printed out to 1 more significant digit than the original values, and standard deviations should be printed out to 2 more significant digits than the original values. The minimum and maximum should report the same significant digits as the original values. For example, for systolic blood pressure:

N	XX
Mean (SD)	XX.X (XX.XX)
Median (Min, Max)	XX.X(XX.X, XX.X)
95% CI	(XX,XX, XX,XX)

- P-values should be output in the format: “0.xxx”, where xxx is the value rounded to 3 decimal places. Any p-value less than 0.001 will be presented as <0.001. If the p-value should be less than 0.0001 then present as <0.0001. If the p-value is returned as >0.999 then present as >0.999
- Percentage values should be printed to one decimal place, in parentheses with no spaces, one space after the count (e.g., 7 (12.8%), 13 (5.4%)). Pre-determine how to display values that round down to 0.0. A common convention is to display as '<0.1', or as appropriate with additional decimal places. Unless otherwise noted, for all percentages, the number of subjects in the analysis set for the treatment group who have an observation will be the denominator. Percentages after zero counts should not be displayed and percentages equating to 100% should be presented as 100%, without any decimal places.

Statistical Analysis Plan

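### In the supplementary Week 12 and Week 20 responder tables, criterion 1 drops first-dose stops whatever their cause, and no stated denominator rule keeps discontinued subjects in as non-responders

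*SAP*

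**What the plan says.** SAP section 9.6 plans three displays of subjects below 6 mg/dL.

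- The first has no eligibility criteria: "The table summarizing the number and % of the subjects maintaining sUA levels below 6 mg/dL at the end of treatment period 3", and likewise at the end of period 5.
- The second and third are introduced as additional tables, for Week 12 (Visit 22) and Week 20 (Visit 32). Each is restricted to a subset defined by four criteria. Criterion 1 is the same in both lists: "Patients received entire 1st doses (without drug discontinuation". Criteria 2 and 3 remove withdrawals of consent and discontinuations for protocol deviations. Criterion 4, also the same in both, reads "Patients did NOT discontinue due to NON-study drug related (OR unlikely to be study drug related) SAE during TP1 or TP2".

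On stopping an infusion, protocol section 8.2.2 says "In the case of a Grade 3 or 4 infusion reactions occurring during an infusion, the administration of study drug should be immediately discontinued". SAP section 5.4 foresees one result of a first-period stop: "Subjects who have a dose interruption during SEL-110 administration in the 1st treatment period and so do not ever receive SEL-037". The same section says of deviations such as partial doses: "Profiles or individual time points with such violations or deviations will be flagged and may be excluded from summary statistics".

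On percentages, the default in SAP section 15.2.5.2, unless otherwise noted, is that "the number of subjects in the analysis set for the treatment group who have an observation will be the denominator". Section 9.3.1 imputes no missing uric acid values, and section 6.1 lists Early Termination data without summarizing them.

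**The concern.** Criteria 2 to 4 remove subjects who left for reasons that say little about the drug, and criterion 4 is worded so that drug-related SAE discontinuations are not removed. Criterion 1 cuts across this. A subject whose first infusion is terminated for a drug-related reaction fails it in the same way as one whose pump broke down.

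A failure caused by the treatment then leaves the denominator, and the subset percentage can look better than the result among all dosed subjects. Cohorts in Parts A and B are planned at 6 to 20 subjects (protocol section 6.2), so one or two such removals can move a cohort's percentage visibly. Readers of a dose-ranging study will look at these percentages cohort by cohort, even though no formal test is attached to them.

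**Working it through.** **1. Who fails criterion 1.** Protocol section 11.2.2.5 records a terminated infusion as "Drug withdrawn (IV infusion was modified through termination of the infusion". Pausing or slowing is a separate category. A paused infusion that is later completed therefore still meets criterion 1, and a terminated one does not. The criterion does not say whether the first dose means SEL-110, SEL-037 or both. In the combination cohorts SEL-110 is given first, so a stop during SEL-110 can mean that SEL-037 is never given.

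**2. Size.** There is no figure in the plan to reproduce: protocol section 12.1 and SAP section 3.6 give no responder rate, stop rate or numerical sample-size calculation. Let n be the subjects dosed in a cohort, r the responders, and k the first-dose stops, all assumed to be non-responders.

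- All-dosed rate: r/n
- Rate after criterion 1: r/(n − k)
- Ratio of the two: n/(n − k)

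With an assumed all-dosed rate of 50%:

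| n | r | r/n | k = 1 | k = 2 | k = 3 |
|---|---|---|---|---|---|
| 20 | 10 | 50.0% | 52.6% | 55.6% | 58.8% |
| 10 | 5 | 50.0% | 55.6% | 62.5% | 71.4% |
| 6 | 3 | 50.0% | 60.0% | 75.0% | 100.0% |

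**3. How often it would arise.** The documents give no rate of first-dose stops, so s is an assumption, shown over a range. The chance of at least one stop in a cohort is 1 − (1 − s)^n. With every stopped subject a non-responder, the relative inflation at a stop fraction s is 1/(1 − s) − 1.

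| s | n = 6 | n = 20 | relative inflation |
|---|---|---|---|
| 2% | 11.4% | 33.2% | 2.0% |
| 5% | 26.5% | 64.2% | 5.3% |
| 10% | 46.9% | 87.8% | 11.1% |
| 20% | 73.8% | 98.8% | 25.0% |

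**4. Is a stopped subject a non-responder?** Very likely, if SEL-037 was never given. Entry requires at least 6 mg/dL at screening (protocol section 7.1). SAP section 5.4 states that SEL-037 alone lowers uric acid, and protocol section 4.3.2.2 reports no effect of SEL-110 alone. Protocol section 6.3.1 allows the next dose in the SEL-110 cohorts only at 1.0 mg/dL or less on Day 21. A subject stopped late in the SEL-037 infusion could still respond. Removing such a subject would lower the percentage: with n = 10 and r = 5, (5 − 1)/(10 − 1) = 44.4%.

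**5. What happens to later discontinuations.** No criterion removes a subject for a drug-related stop at dose 2. But no text counts that subject as a non-responder either. A subject who leaves has no Visit 22 or Visit 32 value, nothing is imputed, and the Early Termination value is not summarized. Under the observation default the subject is absent from the percentage. The same holds for subjects stopped by the Day 21 uric acid rule. Visit 22 is the Period 4 dosing day, so anyone stopped by that rule in Periods 1 to 3 does not reach it. The default applies equally to the table without the four criteria.

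**The case against.** The strongest reply is that these tables are declared subsets and are shown in addition to a table without the criteria, so the fuller result is not replaced. That is correct. A subset of fully exposed subjects also has a pharmacodynamic rationale, because someone who never received SEL-037 says nothing about its activity. First-dose reactions are reported in any case under the primary safety endpoints, which include adverse events leading to discontinuation (SAP section 4.3). What remains is that the fuller table is not a clean safeguard: the observation default and the freedom to exclude partial-dose profiles can remove the same subjects there.

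A reader might also infer more than the documents support:

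- *That a reaction at dose 2 keeps the subject in as a failure, so identical events are handled in opposite ways.* Criterion 4 suggests that intent, but under the denominator and missing-data rules that subject can drop out too.
- *That the comparison of SEL-110 dose levels is biased.* No test or contrast uses these tables. SAP section 9.7 assesses dose effects by mixed models on pharmacodynamic parameters and Day 21 uric acid.
- *That about one subject in five would be stopped.* The 4 of 20 infusion related reactions in protocol section 4.3.2.2 are of any grade, on SEL-110 alone at doses up to 0.5 mg/kg, and are not counts of stopped infusions. For SEL-212, section 4.3.2.3 lists events seen in at least 2 of 31 subjects, and that term is not among them. At most 1 of 31 (3.2%) had it, although related terms such as drug hypersensitivity do appear. Neither figure is a stop rate.
- *That the first-period stops foreseen in SAP section 5.4 are drug reactions.* That item gives no cause. The link comes from protocol section 8.2.2.

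**Conclusion.** The point holds for the two supplementary tables. Criterion 1 removes drug-related first-dose stops, against the evident aim of criterion 4, and the effect is an optimistic descriptive percentage. It is not a breach of an error rate. At an assumed 50% all-dosed rate, one non-responding stop adds 2.6 points at n = 20, 5.6 at n = 10 and 10.0 at n = 6. How often this would occur cannot be derived from the documents, and the direction depends on stopped subjects being non-responders, which is well supported only where SEL-037 was not given.

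The wider gap is that section 9.6 states neither a denominator nor a rule for discontinued subjects. Repairing criterion 1 alone would leave stopped subjects to be dropped by the observation default.

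**What to change.** In SAP section 9.6:

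1. In both lists, limit criterion 1 to first doses left incomplete for a reason unrelated to study drug, such as a pump or line failure or a preparation error. Say whether the first dose means SEL-110, SEL-037 or both.
2. For all the responder tables, override the default of section 15.2.5.2. Use all subjects in the stated set as the denominator, and count as non-responders those who have no visit value because they discontinued for a drug-related event or under the uric acid stopping rule. This is a definition and should be stated as one, since a subject can be stopped by that rule with a value between 1 and 6 mg/dL.
3. Footnote the number excluded by criterion, cohort and reason.

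The cost is a few sentences in the SAP. Causality, action taken, infusion times and volume infused are already collected (protocol sections 11.2.2.2, 11.2.2.5 and 8.3), and protocol section 12.5 leaves the pharmacodynamic analysis to the SAP. No clinical rule changes. The responder percentage becomes slightly less favourable.
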